## **Measurement occasions and follow-up**

Participants will complete a questionnaire package at three time points: baseline (T1), 1 week post intervention (T2) and 3 months post intervention (T3). Long-term change is unlikely if participants do not make initial changes, thus, the 1-week follow-up was selected to assess short-term effectiveness, while still providing participants sufficient time to make their initial planned changes. The 3-month follow-up will assess long-term effectiveness once participants have had several months to reflect on the intervention and implement change. Survey data will be collected and managed using REDCap. Baseline data collection includes socio-demographic data: age, ethnicity, marital status, education, employment, home dwelling type, household income and number of children in the household. Participants will also complete measures to assess primary and secondary outcomes at each time point.

## **Outcome measures**

The primary outcome measure is increase in the total score on the Tolerance of Risk in Play Scale (TRiPS), a 31-item measure examining adults' tolerance of risk during children's play, which has been psychometrically validated [1]. The scale is based on Sandseter's six category model of risky play [2]. Goodness-of-fit statistics for TRiPS have been found to be in the acceptable range [1]. Examination of logical item hierarchy indicated that items that were relatively difficult to endorse (e.g. 'Would you let the child play near the edge of steep cliffs?') were located higher on the hierarchy than those that were easier to endorse (e.g. 'Would you let the child play in the backyard supervised?'). The Person Separation Index was 2.63, indicating that the measure separated persons into more than two distinct groups, such as more and less risk tolerant. The Person Reliability Index was 0.87 indicating that the instrument was able to consistently differentiate between those scoring high versus low. Self-perceived risk tolerance was highly positively associated with scores on TRiPS, and the mean score increased with age of the child [1].

The secondary outcome measure is self-reported behaviour change. Behaviour change is being measured by their self-reported progress on attaining the goal they set for themselves within the RR tool. Participants will be reminded of their goal and asked: 'Did you accomplish your goal?' with 'Yes' and 'No' response options.

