## **Statistical analysis**

Analysis strategy (including verification of model assumptions) will follow Singer and Willet's guidelines [4]. All participants allocated to one of the three conditions will be included in the analysis, regardless of deviation from protocol, missed follow-up observations, or withdrawal. To test our hypotheses that mothers completing either version of the RR tool will have significantly greater increase of tolerance for risk in play, we will compare the two intervention conditions with the control condition. For modelling purposes, we will use mixed-effects models using a correlation structure that assumes model change over time. Selection of the most appropriate model will depend on the distributional form of the data, whether the change is linear and nonlinear and model selection will be based on residual analyses. To test our hypotheses that a higher proportion of mothers in either version of the RR tool will report attainment of behaviour-change goals (secondary outcome measure), we will use logistic regressions.

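### The primary mixed model does not say how baseline TRiPS is handled; if arms keep free T1 means, precision available from data already collected is lost

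*Combined protocol and SAP*

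**What the plan says.** Under Outcome measures: "The primary outcome measure is increase in the total score on the Tolerance of Risk in Play Scale (TRiPS". Under Measurement occasions and follow-up, the questionnaires are given at "baseline (T1), 1 week post intervention (T2) and 3 months post intervention (T3", and "Participants will also complete measures to assess primary and secondary outcomes at each time point", so a T1 TRiPS score is planned for every mother.

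Under Statistical analysis, the hypothesis is that "mothers completing either version of the RR tool will have significantly greater increase of tolerance for risk in play", and to test it "we will compare the two intervention conditions with the control condition". On the model: "we will use mixed-effects models using a correlation structure that assumes model change over time". The form is then left open: "Selection of the most appropriate model will depend on the distributional form of the data", together with whether change is linear and with residual analyses. The same section keeps every allocated participant in the analysis, including those who miss follow-up. Under Missing data, multiple imputation is used for a sensitivity analysis.

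The fixed effects are not written out. T1 TRiPS is not named as a covariate, and no common T1 mean is stated. Nor does the text say that arms have separate T1 means or that simple change scores will be analysed.

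**The concern.** Including T1 as one of the outcome occasions is not the same as adjusting for it. In a model with arm, time and arm-by-time terms, each arm has its own T1 mean. The arm-by-time term then compares changes from those separate means. Under random allocation, T1 means differ only by chance, and a change contrast subtracts the whole of that chance difference. A baseline-adjusted contrast subtracts only the part that predicts follow-up, so it has smaller variance.

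An analyst could follow the Statistical analysis section faithfully, fit the arm-by-time model, and give up this precision on the primary question. The two analyses also give different estimates whenever T1 means differ. As written, that choice could be made after the outcome data have been seen.

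**Working it through.** **The plan's own figure.** There is none to reproduce. The documents state no sample size, power, alpha, SD or correlation between occasions.

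**Inputs from the documents.** Three occasions; TRiPS measured at each; two intervention arms compared with control. The Person Reliability Index of 0.87 (Outcome measures) is not a correlation between occasions and is used only as one point in the range.

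**Inputs assumed.** Random allocation; T1 unaffected by allocation; equal arm sizes; complete data; at first, equal SDs at baseline and follow-up; rho from 0.5 to 0.87.

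**Step 1: visit-specific contrast, one intervention arm against control.** With unit SD:

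- Free T1 means (identical to change scores): variance proportional to 2(1 − rho).
- Common T1 mean (equivalent here to adjusting for T1): variance proportional to 1 − rho².
- Ratio: (1 − rho²) / [2(1 − rho)] = (1 + rho)/2.

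An exact generalised least squares calculation for the T3 contrast gave this ratio under both compound symmetry and AR(1), with rho the T1 to T3 correlation.

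**Step 2: what the ratio means for power.** Suppose, for illustration only, that the change-score contrast has 80% power at two-sided 5%. Power after adjustment is Φ(2.80/√ratio − 1.96).

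| rho | variance ratio | SE ratio | power if 80% with free T1 means |
|---|---|---|---|
| 0.5 | 0.75 | 0.866 | 89.9% |
| 0.7 | 0.85 | 0.922 | 86.0% |
| 0.8 | 0.90 | 0.949 | 84.0% |
| 0.87 | 0.935 | 0.967 | 82.6% |

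**Step 3: if change is modelled as linear.** The plan leaves this open. Taking the occasions as 0, 1 and 13 weeks (assumed) with compound symmetry, the variance of the arm difference in slope with a common intercept, relative to a free intercept, is 0.865 at rho 0.5, 0.93 at 0.7 and 0.97 at 0.87. The savings are about 13.5%, 7% and 3%, against 25%, 15% and 6.5% in Step 2.

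**Step 4: unequal SDs.** With baseline SD s1 and follow-up SD s2, the ratio is s2²(1 − rho²) / (s1² + s2² − 2·rho·s1·s2). At rho 0.7 and s1 = 1:

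- s2 = 0.8: 0.3264/0.52 = 0.63.
- s2 = 1.2: 0.7344/0.76 = 0.97.

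**Step 5: direction.** The change-score variance minus the adjusted variance is proportional to (s1 − rho·s2)², which cannot be negative. Apart from a negligible cost in degrees of freedom, adjustment does not lose precision for a visit-specific contrast, whatever rho and the SDs are.

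**The case against.** The strongest reply is that the plan is silent and has not made a poor choice. Defining the outcome as an increase fixes what is to be estimated, not the estimator; a constrained model also estimates an effect on increase. The planned mixed model is compatible with a common T1 mean, and if one is fitted there is no loss. This stands: a reader might infer that the trial has chosen an unadjusted change analysis and is losing power, and the documents do not support that.

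A reader might also infer bias, through regression to the mean or over-correction of a chance imbalance. Under random allocation both contrasts are unbiased over repeated allocation, so that inference fails too.

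The gain also rests on conditions that the text does not settle. The Statistical analysis section speaks of participants being allocated. The sections available for this review do not describe how, or place T1 relative to allocation. The opening section was not available, so this is not a fault in the plan, but the common-mean constraint does depend on it. The correlation is unknown, and the gain is smaller if change is modelled as linear.

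What the reply does not remove is that the ordinary reading of a mixed model for change in three arms is arm, time and arm-by-time with free T1 means. That model complies with the text and is the less efficient one. Naming the better model is therefore more than filling in a detail.

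**Conclusion.** The point holds conditionally. The plan does not specify how T1 TRiPS enters the primary model. If T1 means are left free, the visit-specific contrast with complete data is the change-score contrast, and the adjusted contrast would need 0.75 to 0.935 of its variance for rho between 0.5 and 0.87, given equal SDs. Under a linear-time model the corresponding range is about 0.865 to 0.97. At high correlation the loss is small; at moderate correlation it is worth having. Because no rho, SD or power is stated, the size for this trial cannot be fixed, and the 80% starting power is only an illustration.

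The conclusion assumes random allocation and a T1 score not affected by it. It concerns efficiency and pre-specification. It does not call the validity of the planned comparison into question. The change should be made because it is almost free.

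**What to change.** In the Statistical analysis section, name the primary model as a constrained longitudinal model, before outcome data are examined:

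- T1, T2 and T3 TRiPS as outcomes, with visit as a category;
- one common T1 mean across the three arms;
- arm-by-visit terms at T2 and T3;
- an unstructured 3×3 covariance.

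Report the differences between each intervention arm and control at T2 and T3 as the effect on increase in TRiPS. Say that the common mean rests on random allocation and on T1 being measured before any effect of allocation, and confirm that both apply.

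This model keeps mothers with only a T1 score in the analysis, in line with the plan's commitment to include all allocated participants. A model for T2 and T3 with T1 as a covariate (and its interaction with visit) is equivalent only when follow-up is complete. With dropout it omits mothers who have no follow-up score, so it should not be offered as interchangeable.

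The cost is SAP wording only, with no new data or procedures. Treating visit as a category also removes the open choice between linear and nonlinear change for the primary comparison.

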## **Adherence to intervention**

Adherence to the risk-reframing (RR) digital tool will be measured by examining the percentage of content viewed, time spent online and task completion [3]. Adherence to the in person RR tool will be measured by examining workshop attendance and task completion.

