## **Missing data**

We will use multiple imputation to manage missing data and will report and justify our imputation strategies. Imputed data for multiple imputation will be analysed as part of a sensitivity analysis.

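### The in-person tool is delivered by workshop, but the analysis makes no allowance for mothers who share a session; if they do, the in-person versus control intervals may be too narrow

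*Combined protocol and SAP*

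**What the plan says.** The reviewed text describes in-person delivery only through its adherence measure, in the section Adherence to intervention: "Adherence to the in person RR tool will be measured by examining workshop attendance and task completion". The digital tool is tracked through online use, and no shared session is described for it. Workshop size, number of workshops and facilitators are not given.

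The section Statistical analysis compares each intervention condition with control. For TRiPS, "we will use mixed-effects models using a correlation structure that assumes model change over time". For goal attainment, "we will use logistic regressions". The strategy is described as "including verification of model assumptions", and "model selection will be based on residual analyses". The analysis set is inclusive: "All participants allocated to one of the three conditions will be included in the analysis, regardless of deviation from protocol".

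Under Outcome measures, "The primary outcome measure is increase in the total score on the Tolerance of Risk in Play Scale". The contrast of interest is therefore one of change from T1.

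**The concern.** A workshop is ordinarily a group event. Mothers who attend together share a facilitator, a discussion and one another's views on risk, so their later outcomes may be more alike than those of mothers from different sessions. The correlation structure named for TRiPS deals with repeated measurements on one mother, not with similarity between mothers. The logistic regressions name no dependence at all.

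If sessions do create such similarity, the in-person arm holds less independent information than its head count suggests, and its contrast with control looks more precise than it is. The digital arm has no such feature, so the two versions of the tool would be judged against control by unequal standards.

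**Working it through.** The plan gives no figure to reproduce: the reviewed text contains no session size, ICC, arm size or power. All numerical inputs below are assumptions, with equal arms, equal total variance and a two-sided 5% test.

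**Closed form for TRiPS.** Let m be the in-person mothers allocated per session, p the share who attend, and ICC the within-session correlation of the change score. Non-attenders count as single mothers.

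- Variance inflation in the in-person arm: DEFF = 1 + p(pm − 1)ICC
- Variance ratio for the contrast with control: f = (DEFF + 1)/2
- True over planned standard error: √f
- Actual type I error: 2[1 − Φ(1.96/√f)]

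Example with m = 10, ICC = 0.05, p = 1: DEFF = 1 + 9 × 0.05 = 1.45; f = 2.45/2 = 1.225; √f = 1.107; 1.96/1.107 = 1.771; type I error 7.7%.

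| m | ICC | DEFF | f | √f | Type I, all attend | Type I, 70% attend |
|---|---|---|---|---|---|---|
| 1, or any m with ICC 0 | – | 1 | 1 | 1 | 5.0% | 5.0% |
| 4 | 0.01 | 1.03 | 1.015 | 1.007 | 5.2% | not computed |
| 8 | 0.02 | 1.14 | 1.07 | 1.034 | 5.8% | 5.4% (f = 1.032) |
| 10 | 0.05 | 1.45 | 1.225 | 1.107 | 7.7% | 6.2% (f = 1.105) |
| 12 | 0.10 | 2.10 | 1.55 | 1.245 | 11.5% | 8.1% (f = 1.259) |

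A separate simulation of a two-arm t-test on a change score, with 10 sessions of 10, gave 4.9% at ICC 0, 7.8% at ICC 0.05 and 10.0% at ICC 0.10. The formula gives 5.0%, 7.7% and 10.4%.

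These error rates refer to a null in which the average effect is zero but sessions vary around it.

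**Goal attainment.** Simulated ordinary logistic (Wald) tests with about 120 per arm and equal true proportions of 0.5 / 0.3 gave 4.4/4.8% at ICC 0. For the four clustered cases in table order they gave 4.7/5.1%, 5.4/5.8%, 7.0/7.7% and 11.1/11.4%. Inflation is negligible at small ICC and similar to TRiPS at the larger values. With partial attendance it was 5.7–5.9% (7 of 10 attending, ICC 0.05) and 7.1–7.6% (8 of 12, ICC 0.10).

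**Does the remedy work?** For TRiPS, a three-occasion REML model with an in-person-only session effect on T2 and T3 and Satterthwaite degrees of freedom gave 4.4% to 5.4%, over seven settings with 5 to 15 sessions. Without the session term the same settings gave 5.0% to 12.9%. A session intercept held constant over T1–T3 is not enough, because it cancels from change: with m = 10, ICC 0.05 and 12 sessions, the model standard error was 0.116 against a true 0.130, and type I error was 8.7%. For goal attainment, CR2 standard errors with Satterthwaite degrees of freedom gave 4.6% to 5.1%.

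**The case against.** The premise rests on one word. The reviewed text has no section on intervention delivery, so its silence on group size or session records cannot be held against the plan. The planned attendance record may already identify the session. No input to the calculation comes from the documents, and the material cases need 10 to 12 mothers per session with ICC 0.05 to 0.10. Verification of assumptions and residual-based model selection also leave room for a session term.

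The null is narrow as well. If the workshop affects nobody, it creates no session correlation and the planned test is valid. If similarity comes only from which session mothers choose, the planned standard error is again right. If inference is meant only for the sessions delivered, the ordinary standard error can be defended. Finally, the goal is one set inside the tool, and the text does not say that control mothers set one, so the goal-attainment figures assume a comparable control outcome.

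Most of this stands as a limit on size and severity. It does not remove the point. Leaving room for a term is not committing to one; residuals can be checked by session only if session membership is known; and a term added after seeing residuals is a data-driven choice in the primary comparison.

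Two stronger readings are tempting. A reader might infer that the in-person comparison is anti-conservative as planned. The documents do not show this, because shared sessions and a positive ICC are not established. A reader might also infer that any clustering pushes both outcomes above 5%. The goal-attainment result of 4.7% at 4 per session and ICC 0.01 (true proportion 0.5) contradicts that.

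**Conclusion.** The point holds conditionally. The Statistical analysis section pre-specifies no allowance for shared workshop sessions for either outcome. If sessions are shared and outcomes within them are positively correlated because of the session, the in-person versus control standard error is understated. In the assumed cases the true value is about 1% to 24% larger, and TRiPS type I error ranges from about 5% to 11.5%, or to 8.1% with 70% attendance. Digital versus control is untouched. Session size, ICC, equal arms and, for goal attainment, a comparable control outcome are all assumed. Severity is low to moderate: group delivery is implied, not stated, and at small sessions or small ICC the effect is close to nil.

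**What to change.** State whether in-person mothers share sessions, and record a session identifier with the planned workshop attendance. If no session has more than one mother, keep the analysis as written. Otherwise pre-specify:

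1. for TRiPS, an in-person-only session random effect on T2 and T3, with Satterthwaite degrees of freedom;
2. for goal attainment, the planned logistic regression with CR2 cluster-robust standard errors and Satterthwaite degrees of freedom;
3. in both, digital, control and non-attending in-person mothers as singletons carrying no shared session effect, so that every allocated mother stays in the analysis.

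The work is one identifier, one variance term and one standard-error option, with no extra participants. The price is precision: a standard error for the in-person versus control contrast about 1% to 24% larger in the assumed clustered cases. Where independent mothers would give 80% power for TRiPS, simulated power with the fix is 78% at ICC 0, 77% (8 per session, 0.02), 69% (10, 0.05) and 56% (12, 0.10) with 10 to 15 sessions. It is 65% and 51% for the last two with 6 and 5 sessions. Much of that loss comes from the clustering itself: the closed form gives 72% for 10 per session and ICC 0.05 once the standard error is correct. If similarity comes only from choice of session, the TRiPS fix is mildly conservative (4.1% to 4.3% at ICC 0.05).

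Two parts were not tested. The first is the corrected analyses under partial attendance. The second is whether the session identifier should enter the imputation model for the sensitivity analysis ("We will use multiple imputation to manage missing data and will report and justify our imputation strategies"). The latter should be decided when the imputation strategy is written.

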## **Statistical analysis**

Analysis strategy (including verification of model assumptions) will follow Singer and Willet's guidelines [4]. All participants allocated to one of the three conditions will be included in the analysis, regardless of deviation from protocol, missed follow-up observations, or withdrawal. To test our hypotheses that mothers completing either version of the RR tool will have significantly greater increase of tolerance for risk in play, we will compare the two intervention conditions with the control condition. For modelling purposes, we will use mixed-effects models using a correlation structure that assumes model change over time. Selection of the most appropriate model will depend on the distributional form of the data, whether the change is linear and nonlinear and model selection will be based on residual analyses. To test our hypotheses that a higher proportion of mothers in either version of the RR tool will report attainment of behaviour-change goals (secondary outcome measure), we will use logistic regressions.

## **Missing data**

We will use multiple imputation to manage missing data and will report and justify our imputation strategies. Imputed data for multiple imputation will be analysed as part of a sensitivity analysis.

## **Statistical software**

The latest version of R (R Foundation for Statistical Computing, Vienna, Austria) and Stata (StataCorp LLC, College Station, TX, USA) will be used for statistical analysis and graphics.

